#### 10.4.2.2 Laboratory Assessments for Cytokine Release Syndrome

Blood (plasma) samples will be collected at Screening and as clinically indicated ([Section 9.5.5](#)) for assessment of IFN- $\gamma$ , IL-6, IL-1, TNF- $\alpha$ , C-reactive protein, and ferritin. If CRS is suspected, a blood (plasma) sample should be collected within 5 hours (or as soon as possible) after

occurrence of the event, and 1 week after occurrence of the event. Samples will be shipped to the central laboratories for analysis.

### **10.4.3 Drug Concentration Measurements**

[Sample acquisition removed by Amendment 4]

### **10.4.4 Biomarker Assessments**

[Sample acquisition removed by Amendment 4]

Evaluations that may be performed in this study include but are not limited to:

- Measurement of systemic cytokines to assess PD
- Determine relationship of STING genotype to response
- Assess gene expression changes in the TME and the periphery
- Determine phenotype and function of immune cells
- Assessment of TME markers associated with immune infiltrate in injected and distal lesions

#### **10.4.4.1 Pharmacogenetic Sample**

[Sample acquisition removed by Amendment 4]

#### **10.4.4.2 Tumor Tissue (Biopsy)**

[Sample acquisition removed by Amendment 4]

#### **10.4.4.3 Pharmacodynamics, Biomarkers, and Indicators of Biological Activity**

[Sample acquisition removed by Amendment 4]

Additional analytical assessments and methodologies may be used to understand the mechanism of action ADU-S100 and pembrolizumab, or to understand factors associated with response or cancer progression. These tests may be performed at the Sponsor's discretion and may include: additional phenotyping and cellular function analysis in the periphery; and gene expression changes in the tumor or periphery.

## **10.5 Appropriateness of Measures**

Clinical indicators of efficacy will be evaluated using RECIST v1.1 criteria for tumor response assessments, which are widely accepted as uniform response criteria for HNSCC. Since immunotherapeutic agents may produce antitumor effects by potentiating endogenous cancer-specific immune responses, tumor response will also be evaluated using iRECIST. These response patterns may extend beyond the typical time course of responses seen with cytotoxic

agents and can manifest a clinical response after an initial increase in tumor burden or even the appearance of new lesions.

Assessments of progression-free and overall survival are also planned; PFS and OS are objective, direct measures of benefit, although interpretation may not only be limited by the size of the data set but also confounded by subsequent anti-cancer therapies and non-cancer deaths.

The safety parameters to be evaluated in this study include standard assessments such as recording of medical history, AEs and SAEs, physical examination, vital signs, ECGs, serum chemistry and hematology, urinalysis, concomitant medications, and other routine clinical and laboratory procedures.

The criteria for dose modification or treatment discontinuation are based on available clinical and nonclinical data for ADU-S100 combined with clinical experience and label language for pembrolizumab, and general practices in the development of immunotherapeutic agents. Since the safety profile of ADU-S100 has not been fully characterized and pembrolizumab is associated with serious risks, additional safety precautions (i.e. dosing eligibility and extended safety-reporting period) have been included to monitor subject safety.

As may occur with any immunotherapeutic agent, ADU-S100 may elicit an immune response resulting in CRS. Subjects will therefore be monitored at baseline and as clinically indicated for cytokine levels as added safety measure ([Section 9.5.5](#)).

Pre-treatment and on-treatment blood samples and tumor biopsies will provide an initial investigation into the mechanism of action of ADU-S100 when administered with pembrolizumab. Characterization of a broad panel of biomarkers may be predictive of response to therapy and may also give insight into appropriate endpoints in additional clinical studies.

## 11 ADVERSE EVENT REPORTING

AEs, SAEs, and pregnancy occurring during the protocol-specified timeframes defined in [Section 10.3.5](#) will be assessed and reported following guidelines provided in the following sections.

### 11.1 Adverse Events

An AE is defined as any untoward medical occurrence associated with the use of a drug in humans, whether or not considered drug related. An AE can therefore be any unfavorable and/or unintended sign (including an abnormal laboratory finding), symptom, or disease temporally associated with the use of an investigational medicinal product, whether or not related to the investigational medicinal product.

Subjects should be instructed to report any AE that they experience to the Investigator. At each indicated visit, Investigators will assess for AEs. AEs will be monitored and documented on the AE eCRF.

Wherever possible, a specific disease or syndrome rather than individual associated signs and symptoms should be identified by the Investigator and recorded on the eCRF. However, if an observed or reported sign or symptom is not considered a component of a specific disease or syndrome by the Investigator, it should be recorded as a separate AE on the eCRF. Additionally, the condition that led to a medical or surgical procedure (e.g. surgery, endoscopy, tooth extraction, or transfusion) should be recorded as the AE term, not the procedure.

For existing medical conditions reported as part of the medical history, clinically significant changes in signs or symptoms, or change in severity or seriousness should be reported as an AE.

Clinically significant abnormal laboratory or other examination (e.g. ECG) findings that are detected during the study or are present at Screening and significantly worsen during the study should be reported as AEs. The Investigator will exercise his or her medical and scientific judgment in deciding whether an abnormal laboratory finding or other abnormal assessment is clinically significant. Any abnormal test that is determined to be an error does not require reporting as an AE.

Examples of AEs include the following:

- Exacerbation of a chronic or intermittent preexisting condition, including an increase in frequency or intensity of the condition
- Signs, symptoms, or the clinical sequelae of a suspected interaction with another medical product
- Signs, symptoms, or the clinical sequelae of a suspected overdose of either investigational agent or a concurrent medication.

Examples of AEs do not include the following:

- Medical or surgical procedures (e.g. endoscopy, appendectomy); instead, the medical condition that led to the procedure is the AE term
- Situations that are unwanted but in which an untoward medical occurrence did not occur (e.g. admissions for respite care)
- Anticipated day-to-day fluctuations of a pre-existing disease or condition (present or detected before enrollment) that does not worsen overall

### 11.1.1 Disease-Related Events

The term "disease progression" should be recorded as an AE only if there are no other identifiable AEs associated with the disease progression at the time of reporting. For events associated with disease progression, the relevant signs and symptoms should be reported using a diagnosis whenever possible rather than individual underlying signs and symptoms. When a clear diagnosis cannot be identified, each sign or symptom should be reported as a separate AE. If the events resulting from disease progression meet the criteria for an SAE (e.g. resulted in hospitalization, a life-threatening event, or death), the specific event(s) should be reported as an SAE(s).

### 11.1.2 Assessment of Adverse Events by the Investigator

The Investigator will assess the severity (intensity) of each AE and the potential relationship between the AE and the study drug(s).

#### 11.1.2.1 Assessment of Severity

The severity of all AEs should be graded according to the National Cancer Institute Common Terminology Criteria for Adverse Events (NCI-CTCAE v. 5.0; <http://ctep.cancer.gov/reporting/ctc.html>). For AEs not listed in the CTCAE, the following grading system should be used:

- Mild (CTCAE Grade 1): Mild; asymptomatic or mild symptoms; clinical or diagnostic observations only; intervention not indicated
- Moderate (CTCAE Grade 2): Moderate; minimal, local or noninvasive intervention indicated; limiting instrumental activities of daily living
- Severe (CTCAE Grade 3): Severe or medically significant but not immediately life-threatening; hospitalization or prolongation of hospitalization indicated; disabling; limiting self-care activities of daily living
- Life-threatening (CTCAE Grade 4): Life-threatening consequences; urgent intervention indicated
- Death (CTCAE Grade 5): Death related to AE

### 11.1.2.2 Assessment of Attribution

The Investigator is obligated to estimate the relationship between the study drug(s) and the occurrence of each AE or SAE. The relationship (synonym: causality) is based on the Investigator's clinical judgment regarding the likelihood that study drug caused the AE and may include consideration of some or all of the following factors:

- Alternative possible causes of the AE, including the subject's underlying disease or co-morbid conditions, other drugs, or other host and environmental factors
- The temporal sequence between the exposure to study drug and the AE
- Whether the clinical or laboratory manifestations of the AE are consistent with known actions or toxicity of the study drug
- Whether the AE resolved or improved with decreasing the dose or stopping the study drug (i.e. dechallenge); or recurred or worsened with re-exposure to the drug (i.e. rechallenge).

The Investigator should consult the IB in the determination of the assessment. The Investigator should consider all possible etiologies for the AE and render a causality assessment based on the most likely contributing factor to the AE.

There may be situations when an SAE has occurred and the Investigator has minimal information to include in the initial report. However, the Investigator must assess causality for every event before the transmission of the SAE. The Investigator may change his or her opinion of the causality in light of follow-up information, amending the SAE report.

The assessment of the relationship between the AE and the study drug will be determined using one of the following attribution categories:

RELATIONSHIP	DESCRIPTION
Unrelated to investigational agent/intervention	The AE is clearly NOT related to the intervention
	The AE is doubtfully related to the intervention
Related to investigational agent/intervention	The AE may be related to the intervention
	The AE is likely related to the intervention
	The AE is clearly related to the intervention

AEs listed as related are considered to have a suspected "reasonable causal relationship" to the investigational agent/intervention (ICH E2A). Per the ICH E2A and FDA guidelines, the expression "reasonable causal relationship" is meant to convey in general that there are facts (evidence) or arguments to suggest a causal relationship.

Additional guidelines in describing relationship:

- Related AEs follow a reasonable temporal sequence from the study drug administration and cannot be excluded as possibly or probably being caused by the study drug (e.g.

existence of similar reports attributed to the suspected drug and/or its analogues; reactions attributable to the pharmacologic effect of the drug) and can be excluded as possibly being caused by other factors such as underlying disease, complications, concomitant drugs, or concurrent treatment. The AE can be fully explained by the administration of study drug.

- Not Related: AE does not follow a reasonable temporal sequence from the study drug administration and can be reasonably explained by other factors, including underlying disease, complications, concomitant drugs, or concurrent treatment. Another factor is clearly the cause of the AE.
- For AEs occurring prior to initiation of study drug administration, the Investigator will assess relationship between the event and the protocol-required study procedures.

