### 7.5.2 *Adverse Events*

Treatment-emergent adverse events are defined as those AEs with onset after the first dose of either study drug or existing events that worsened after the first dose during the study. Treatment-emergent AEs will be summarized for all subjects combined. Events reported with a partial onset date (eg, month and year are reported but the day is missing) will be considered to be treatment-emergent if it cannot be confirmed that the event onset was prior to the first dose of either study drug based on the available date entries.

Verbatim terms on case report forms will be mapped to preferred terms and system organ classes using the Medical Dictionary for Regulatory Activities (MedDRA, version 23.0). Adverse events will be graded according to the National Cancer Institute Common Terminology Criteria for Adverse Events (NCI-CTCAE).

Summaries that are displayed by system organ class and preferred terms will be ordered by descending incidence of system organ class and preferred term within each system organ class. Summaries displayed by preferred term only will be ordered by descending incidence of preferred term. Summaries of the following types will be presented:

- Overall summary of number of unique TEAEs and treatment-emergent SAEs and subject incidence of TEAEs meeting various criteria;
- Subject incidence of TEAEs by MedDRA system organ class and preferred term;
- Subject incidence of the most frequently-occurring TEAEs (ie, TEAEs occurring in  $\geq 10\%$  of the All Treated Population) by MedDRA preferred term;
- Subject incidence of TEAEs by NCI-CTCAE grade, MedDRA system organ class, and preferred term;
- Subject incidence of TEAEs related to each study drug and both study drugs by NCI-CTCAE grade, MedDRA system organ class, and preferred term;
- Subject incidence of TEAEs by relationship to each study drug, MedDRA system organ class, and preferred term;
- Subject incidence of the most frequently-occurring TEAEs related to each study drug and both study drugs (ie, related TEAEs occurring in  $\geq 10\%$  of the All Treated Population) by MedDRA preferred term;
- Subject incidence of TEAEs with NCI-CTCAE grade  $\geq 3$  and related to each study drug and both study drugs by MedDRA system organ class and preferred term;

- Subject incidence of treatment-emergent SAEs by MedDRA system organ class and preferred term;

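### Protocol Section 11.1.2.2 gives two incompatible tests for a related adverse event, and a well-timed event with a second plausible cause meets only one of them

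*Protocol*

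**What the plan says.** Protocol Section 11.1.2.2 has the investigator assign each AE to one of five descriptions under two headings. Clearly not related and doubtfully related count as unrelated. The other three, starting with "may be related", count as related. The sentence after the table begins "AEs listed as related are considered to have a suspected" and goes on to the ICH E2A idea of a reasonable causal relationship, which it explains as meaning that "there are facts (evidence) or arguments to suggest a causal relationship".

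The additional guidelines that follow define the same two classes again. A Related AE must have a reasonable time sequence, must be one for which study drug cannot be ruled out, "and can be excluded as possibly being caused by other factors such as underlying disease, complications, concomitant drugs, or concurrent treatment". The bullet ends: "The AE can be fully explained by the administration of study drug". The Not Related bullet applies where the "AE does not follow a reasonable temporal sequence from the study drug administration and can be reasonably explained by other factors", and adds that another factor is clearly the cause.

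Earlier in the section a third standard appears: the investigator is to "render a causality assessment based on the most likely contributing factor to the AE".

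SAP Section 7.5.2 plans tables by relationship to each drug, and also "Subject incidence of TEAEs related to each study drug and both study drugs by NCI-CTCAE grade". The related serious-AE tables use the same split.

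**The concern.** A category for events that may be related is needed mainly for events with some other possible cause. The exclusion condition in the guidelines removes that category from the related side. Two investigators who each follow the written text can then classify the same event differently.

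The design makes such events likely. Every subject is to receive both agents, and both are given on Day 1 of each cycle (Protocol Sections 9.3 and 9.4.2.2). Section 5.4 describes immune-mediated reactions with pembrolizumab and possible systemic immune activation with ADU-S100, and Section 9.5.5 notes that cytokine release syndrome can be hard to tell apart from other conditions.

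Relatedness decides which unexpected serious AEs are expedited (Section 11.3.3), which new AEs and serious AEs are reported after the window closes (Table 10-1), and which events enter the SAP's related-event tables.

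**Working it through.** There is no figure to reproduce. The check applies each written test to a few typical events.

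The conditions in the guidelines are:

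- Related: (a) reasonable time sequence, and (b) study drug not ruled out, and (c) other causes ruled out, with (d) the event fully explained by study drug.
- Not Related: (e) no reasonable time sequence, and (f) reasonably explained by other factors, with (g) another factor clearly the cause.

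| Event | Category table | Guidelines: Related | Guidelines: Not Related | Class under the guidelines |
|---|---|---|---|---|
| 1. Well timed, no other plausible cause | Related | met | fails (e) | Related |
| 2. Well timed, plausible for study drug and for the cancer or another medicine | Related (may be) | fails (c) | fails (e) and (g) | none |
| 3. Well timed, plausible for both study drugs, each judged separately, partner counted as concurrent treatment | Related to each | fails (c) for each drug | fails (e) and (g) | none, for either drug |
| 4. As 3, but the two drugs pooled as study drug | Related | can be met | fails (e) | Related |
| 5. Well timed, link judged doubtful | Unrelated | fails (d) | fails (e) | none |

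Three results follow.

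- Row 2 shows the basic conflict. It does not depend on there being two study drugs, because underlying disease is enough to trigger it.
- Rows 3 and 4 show that the two-drug consequence depends on whether the partner drug is an outside factor. Under row 3, no event can be attributed to both agents, so the SAP tables for both study drugs, read as counts of events attributed to both, could not be filled.
- Row 5 shows that the Not Related bullet is also out of line with the table. The table treats a doubtful link as unrelated, but the bullet withholds that class whenever the timing is reasonable.

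In rows 2, 3 and 5 the guidelines give no class. They do not call these events unrelated.

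**The case against.** The strongest reply is that the table already governs. Section 11.1.2.2 says that the assessment is made with its categories, the later bullets are only additional guidance, and alternative causes are among the factors that clinical judgment may weigh. This is a fair account of the likely intent, but it does not remove a written condition that contradicts the table.

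The second reply concerns the partner drug. The Definition of Terms in Protocol Section 4 makes study drug interchangeable between the two agents. Section 10.3.6 describes concomitant medications without listing the study drugs, and concurrent treatment is not defined. The partner drug therefore need not be an outside factor. This stands, and it makes row 3 conditional. It does not settle the matter, because attribution is needed by drug: SAP Section 7.5.2 tabulates it that way, and Protocol Section 9.5 refers to a relationship with ADU-S100 and to toxicity attributable to pembrolizumab.

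The third reply concerns safety. All serious AEs go to the sponsor within 24 hours whatever their cause (Section 11.3.1). The general Grade 3 and Grade 4 rows of Table 9-2 do not depend on relatedness, and the SAP also tabulates all treatment-emergent AEs and serious AEs regardless of relationship. This stands. A reader might infer that serious events would go uncollected or that the trial has a patient-safety failure. The documents do not support that.

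A reader might also try to size the effect from Section 5.2.2, which reports treatment-related serious AEs in 3 of 16 treated patients, by supposing that the strict wording would turn this into 0 of 16 for ADU-S100. That does not work. The section does not attribute those events to one drug or the other. They were called related although the trial gives both drugs, so they are no evidence that investigators apply the exclusion literally. If the present wording was in force, 3 of 16 already contains its effect and is not an upper limit.

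**Conclusion.** The conflict is real and is plain on the text. The table and the guidelines cannot both be followed for a well-timed AE with a second plausible cause. Related-AE counts may be too low, or may differ between sites according to which text was used, and so may the expedited and out-of-window reporting that depends on relatedness. No numerical size can be derived from the documents, and no efficacy result or sample-size figure is affected.

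The statement that an event plausible for both drugs is related to neither rests on two assumptions: attribution is made drug by drug, and the partner drug counts as concurrent treatment. Even then the event is left unclassified, because it fails Not Related as well. A reader might infer a one-sided under-count, but the gap by itself does not fix how sites resolve it.

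**What to change.** Reconcile the two parts of Section 11.1.2.2:

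- Make the category table the single operative definition.
- Remove from the Related bullet the condition that other causes be excluded and the sentence requiring full explanation by study drug.
- Align the Not Related bullet with the table's two unrelated descriptions.
- State that another possible cause, including the other study drug, does not by itself make an AE unrelated.
- State that relationship is recorded separately for each drug, so that the SAP's tables for each drug and for both can be filled.

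The cost is a protocol clarification and a memo to sites. Related-AE rates may rise slightly. Because 16 subjects had been treated by 17 December 2020 (Section 5.2.2), out of a planned maximum of 20, a change made now could mix two standards in one table. Earlier attributions should be re-checked against the single definition, or the clinical study report should state when the definition changed.

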### 11.1.3 Adverse Event Follow-up

Follow-up is required for all subjects with AEs until the event has been resolved or the condition has stabilized. Clinically significant abnormal laboratory values occurring during the clinical trial or at the EOT Visits should be followed until repeat tests return to normal, stabilize, or are no longer clinically significant.

## 11.2 Serious Adverse Events

An AE or adverse reaction is considered serious if, in the view of either the Investigator or Sponsor, it results in any of the following outcomes:

- Death
- A life-threatening AE
  - NOTE: An AE or adverse reaction is considered “life-threatening” if, in view of either the Investigator or Sponsor, its occurrence places the subject at immediate risk of death. It does not include an event that, had it occurred in a more severe form, might have caused death.
- Requires hospitalization or prolongation of existing hospitalization
  - NOTE: Any hospital admission with at least one overnight stay will be considered an inpatient hospitalization. An emergency room visit without hospital admission will not be recorded as an SAE under this criterion, nor will hospitalization for a procedure scheduled or planned before signing of informed consent. However, unexpected complications and/or prolongation of hospitalization that occur during elective surgery should be recorded as AEs and assessed for seriousness. Admission to the hospital for social or situational reasons (i.e. no place to stay, live too far away to come for hospital visits) or for observation post-study drug administration will not be considered a SAE.
- A persistent or significant incapacity or substantial disruption of the ability to conduct normal life functions
- A congenital anomaly/birth defect

- An important medical event.
  - NOTE: Important medical events that may not result in death, be life-threatening, or require hospitalization may be considered an SAE when, based upon appropriate medical judgment, they may jeopardize the subject and/or may require medical or surgical intervention to prevent one of the outcomes listed above. Examples of such medical events include allergic bronchospasm requiring intensive treatment in an emergency room or at home, blood dyscrasias or convulsions that do not result in inpatient hospitalizations, or the development of drug dependency.

